As this is a single-arm study, no randomization will occur, and no blinding procedures are required.

4 Interval Windows

Interval windows for the purpose of analysis in this study will not be defined outside of those already specified in the protocol for visit scheduling as the collection of data for the primary and secondary performance endpoints occurs intra-operatively. The final visit occurs approximately 4 weeks after surgery, thus no interval windows need to be defined given the absence of long-term follow-up in this study. The Schedule of Events specifies a window of 14 days around the scheduling of the 4-week follow-up visit, and any information entered in the eCRFs at this visit will correspond to the 4-week visit. There will be no assigning of observations to time points outside of the visit to which they are recorded in the eCRFs.

5 Levels of Significance

The statistical hypothesis for the primary endpoint will be evaluated using a one-sided significance level of 0.025. A 95% confidence interval will be provided for the primary endpoint. Estimation of primary endpoint by procedure group and procedure subgroup will provide 95% confidence interval. Estimation of secondary and safety endpoints will be summarized by number and percentages only.

6 Analysis Sets

Full Analysis Set: Full Analysis Set (FAS) will include subjects for whom the ENSEAL X1 device is utilized during the surgical procedure and have assessment for the primary endpoint. The FAS includes subjects for whom the answer is "Yes" to at least one of the following questions from the "ENSEAL X1 Usage" form on eCRF: "Were adhesions removed or divided by ENSEAL X1", "Were lymphatics bundles divided by ENSEAL X1", "Were tissue bundles divided by ENSEAL X1", "Was the ENSEAL X1 used for tissue grasping", "Was the ENSEAL X1 used for tissue dissection." The summary of all primary and secondary performance endpoints will be performed using FAS by procedure group (upper GI, lower GI, and gynecological), procedure subgroup (fundoplication, gall bladder, sleeve gastrectomy, and small intestine resection) and on the entire pooled set of subjects.

Safety Analysis Set: The Safety Analysis Set (SAS) will include all subjects who signed informed consent and for whom the ENSEAL X1 device is utilized during the surgical procedure. The safety endpoints will be summarized using SAS by procedure group, procedure subgroup and in total.

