All Enrolled Set: The All Enrolled Set (AES) contains all subjects who provide informed consent for this study. The AES will be used for disposition of study subjects and for all listings.

7 Sample Size Justification

A sample size of at least 230 vessel transections is required to have a minimum of 90% power for rejecting the null hypothesis when the expected rate of Grade 3 hemostatic transections is at least 94.0% based on exact binomial test and a one-sided significance level of 0.025. The hemostatic transection grades for vessels are assumed to be independent within a subject and within a procedure.

In order to achieve a total of 230 vessel transections for analysis with a minimum of 27 vessel transections in each group (including 4 procedure subgroups in upper GI procedure), a minimum of 122 subjects (a maximum of 149 subjects) will be enrolled in the study.

The original sample size of the study was based on the assumption of one vessel transection per subject. At the time of amendment 5 the number of transections per subject was estimated to be 1.9 on average. The primary endpoint and the study hypothesis are based on hemostasis of vessel transection; therefore, the number of subject to be enrolled was updated to ensure 230 vessel transections.

Given that the primary endpoint is being evaluated intra-operatively, it is not anticipated that there will be subject dropout prior to evaluating this endpoint, thus no adjustment or increase in subject enrollment is planned to account for dropout. A minimum of 27 vessel transections in each group (including 4 procedure subgroups in upper GI procedure) is planned to attain optimum representation of each of the procedure groups to the whole study sample.

From a safety perspective on the pooled analysis of 133 subjects and in consideration of rare AEs that may occur (e.g., bleeding requiring blood product transfusion), for an event that has an incidence rate of, for example, 1%, then in a sample of 133 subjects, the probability of observing at least 1 event is 73.7% under a binomial probability model. Thus, this sample size provides a high probability of observing rare events if they do occur, and provides reasonable assurance to conclude that the likelihood of such AEs is less than 2.8% if they do not occur based on the upper limit of an exact 95% confidence interval when 0 events out of 133 subjects are observed.

8 Analyses to be Conducted

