8.4 Primary and Secondary Endpoints and Associated Hypotheses

8.4.1 Primary Endpoint and Associated Hypotheses

The primary performance endpoint in this study is the number and percentage of vessels where hemostasis (\leq Grade 3) is achieved using the ENSEAL X1 device. The hemostasis grading scale is defined as:

- Grade 1: no bleeding at transection site;
- Grade 2: minor bleeding at transection site, no intervention needed;
- Grade 3: minor bleeding at transection site, mild intervention needed, use of compression, basic energy devices (monopolar and/or bipolar device), and/or touchups with ENSEAL X1.
- Grade 4: significant bleeding (e.g., pulsatile blood flow, venous pooling) requiring intervention such as extensive coagulation or ligation with use of additional hemostatic measures (e.g., hemoclips, staples, sutures, fibrin sealants, other advanced energy products).

The primary performance endpoint will be summarized at the vessel transection level as multiple vessel transections per subject is expected; that is, the denominator for the primary endpoint will be the total number of vessel transections and the numerator will be the number of vessel transections where hemostasis (\leq Grade 3) is achieved.

The following hypothesis will be evaluated for the primary endpoint:

H₀:
$$p \le 87.5\%$$

H₁: $p > 87.5\%$

Where *p* is the percentage of transections achieving a Grade 3 or lower hemostasis rating and 87.5% is set as a performance goal for the lower bound of acceptable hemostasis. A 95% confidence interval will be calculated for *p* based on the proportion of vessel transections where Grade 3 or lower hemostasis is achieved using Clopper-Pearson's method and the lower limit of this confidence interval will be compared to 87.5% to evaluate the above hypotheses. A p-value will be determined based on an exact binomial test. Primary endpoint will be evaluated for the total sample. For procedure group and procedure subgroup 95% CI will be provided using Clopper-Pearson's method for proportion of vessel transections where Grade 3 or lower hemostasis is achieved.

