8.8 Sensitivity Analyses

The analysis of the primary performance endpoint described above in Section 8.4.1 makes the assumption of independence of activations within a subject in estimating the variance for the confidence interval. Achieving hemostasis (\leq Grades 3) may be correlated within a patient for those with two or more vessel transections. To account for the potential dependence in achieving

hemostasis in vessels within a subject, a sensitivity analysis will be performed where the 95% confidence interval will be estimated using a generalized linear mixed model. The underlying distribution of the dependent variable in the model is logistic as the outcome variable is binary (i.e., hemostasis achieved or not achieved). A random intercept term at subject-level will be used in the generalized linear mixed model to account for the within subject correlation in achieving hemostasis. The distribution of the random intercept is assumed to be Gaussian.

If the inference from the mixed model is not consistent with the inference from the primary endpoint analysis as described in Section 8.4.1 then the inference from the mixed model will be used to evaluate success.

Example SAS code:

*Create a pseudo variable group so that the 95% CI for intercept can be estimated;
data mydata; set mydata; group="pseudo"; run;

PROC GLIMMIX DATA = mydata;
CLASS id group;
MODEL OUTCOME (Event='0') = group / S DIST=BINARY LINK=LOGIT;
RANDOM intercept / SUBJECT = id;
LSMEANS group / CL ILINK; *The results of interest (95% CI of rate of hemostasis) are presented on the last two columns;
RUN;

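### SAP 8.8 lets a mixed model decide success, but as coded it adds almost no protection against within-subject correlation beyond the exact test

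*SAP*

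**What the plan says.** SAP 8.4.1 defines p as the percentage of all transections reaching Grade 3 or lower. It tests p with an exact binomial test and a Clopper-Pearson interval; "87.5% is set as a performance goal for the lower bound of acceptable hemostasis". SAP 5 sets the level: "The statistical hypothesis for the primary endpoint will be evaluated using a one-sided significance level of 0.025". SAP 7 sizes the study on independent vessels and notes that "the number of transections per subject was estimated to be 1.9 on average".

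SAP 8.8 accepts that outcomes within a subject may be correlated: "a sensitivity analysis will be performed where the 95% confidence interval will be estimated using a generalized linear mixed model". The model is logistic with a Gaussian random intercept per subject. The code is labelled an example, begins "PROC GLIMMIX DATA = mydata", carries no METHOD= option, and takes the interval from LSMEANS with ILINK. The text names no estimation method either. If the two inferences differ, "the inference from the mixed model will be used to evaluate success".

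Protocol 5.4 and 5.9.4 leave the handling of correlation to the SAP, so SAP 8.8 is the only place where it is specified.

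**The concern.** The override rule makes the mixed model the deciding analysis in every case. If it agrees with the exact test, nothing changes; if it disagrees, it wins. Success is therefore whatever the mixed model says, and the override can turn a failure into a success as well as the reverse.

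Two features of the code work against its purpose.

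- **Estimation method.** With none named, the procedure uses its default, a linearised (restricted, subject-specific) pseudo-likelihood. That method is known to shrink the variance component when clusters are small and outcomes are binary.
- **Target.** ILINK applied to the LS-mean gives the rate for a subject whose random effect is zero. When p is high and subjects vary, that rate lies above the proportion of transections that SAP 8.4.1 calls p.

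At stake is whether the analysis meant to guard against correlated vessels holds the 2.5% one-sided error when vessels are in fact correlated.

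**Working it through.** **Inputs from the documents.** Null rate 87.5% (SAP 8.4.1); expected rate 94.0%, 230 transections and 1.9 transections per subject (SAP 7); one-sided 0.025 (SAP 5). Minimum subjects: 122 in SAP 7, 133 in SAP 1.2 and the protocol, so both were used. Outcome 0 is read as hemostasis achieved, as the code comment implies.

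**Assumptions not in the documents.** Subject variance 0.5, 1, 2 or 4 on the logit scale, which at a marginal rate of 87.5% gives ICC 0.055, 0.105, 0.189 or 0.306. Cluster sizes are 1 + Poisson(0.9) or a right-skewed pattern, both with mean 1.9. The default fit was recoded; SAS itself was not run.

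**Step 1, the plan's own figure.** With 230 independent transections the exact rule is success at 212 or more. P(X ≥ 212 | 0.875) = 0.0161 and P(X ≥ 212 | 0.94) = 0.9002, so the stated 90% power is reproduced. 230/1.9 = 121.05, or 122 subjects; 133 × 1.9 = 252.7 transections.

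**Step 2, variance recovered by the default fit.** Large-sample ratio of estimate to truth: 0.50–0.65 at variance 0.5, 0.45–0.54 at 1, 0.37–0.43 at 2, 0.28–0.31 at 4. Median ratios at 122 subjects and the null rate are similar: 0.44–0.47, 0.36–0.39 and 0.28–0.30 for variances 1, 2 and 4.

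**Step 3, width of the interval.** Standard errors on the logit scale, null rate, 122 subjects. Share of inflation = (default − naive) / (empirical SD − naive).

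| Sizes, variance | Naive | Default | Robust | Empirical SD | Share |
|---|---|---|---|---|---|
| Poisson, 2 | 0.202 | 0.223 | 0.224 | 0.231 | 0.021/0.029 = 0.72 |
| Skewed, 2 | 0.202 | 0.230 | 0.236 | 0.238 | 0.028/0.036 = 0.78 |
| Skewed, 4 | 0.202 | 0.244 | 0.254 | 0.266 | 0.042/0.064 = 0.66 |

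Across variances 1, 2 and 4 and both patterns the share is about 65–86%. Width is not the main failure.

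**Step 4, centre of the interval.** With true p = 0.875, the rate at random effect zero is 0.929 at variance 2 and 0.955 at variance 4. The default fit shrinks the intercept too, so it reports on average 0.881–0.882 and 0.885–0.887. At variance 4, taking 0.887: ln(0.887/0.113) − ln(0.875/0.125) = 2.061 − 1.946 = 0.115, or 0.115/0.244 = 0.47 of a standard error in the favourable direction.

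**Step 5, one-sided error at p = 87.5%.** 122 subjects, 6,000 trials per case (Monte Carlo SE at 2.5%: √(0.025 × 0.975/6000) = 0.2 points).

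| ICC | Default model (Poisson / skewed) | Exact test (Poisson / skewed) | Robust (skewed) |
|---|---|---|---|
| 0.055 | 2.3% / 2.1% | 2.4% / 2.4% | 2.1% |
| 0.105 | 2.5% / 3.1% | 2.6% / 3.3% | 2.5% |
| 0.189 | 3.5% / 4.0% | 3.2% / 3.8% | 2.7% |
| 0.306 | 5.2% / 6.3% | 4.1% / 5.5% | 3.2% |

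Three smaller runs with 133 subjects (800 to 1,200 trials; ICC 0.1 / 0.2 / 0.3) agree within simulation error. The default model gave 1.8/3.4/5.8%, 3.2/3.5/5.6% and 2.4/5.6/4.2%. The robust interval gave 1.3/2.3/2.3%, 2.4/2.5/2.6% and 2.0/2.8/1.8%.

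**Step 6, how often the override acts.** At the null rate it changes the exact verdict in only 0.2–2.4% of trials. In the skewed case at variance 4, failure becomes success in 1.62% of trials and success becomes failure in 0.80%; at variance 2 the figures are 0.67% and 0.52%.

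**Step 7, partial repairs.**

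- Quadrature with ILINK unchanged: false passes of 2.9/6.4/18.8% at ICC 0.1/0.2/0.3 (133 subjects). With 122 subjects, 15.3% at variance 4, and power at 94% of only 0.47–0.53.
- Rate averaged over subjects, default fit kept: coverage at 94% of 84/72/63%, power 66/49/41%.
- Both changes together: coverage 96/95/95%, power 89/85/81%.

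**The case against.** The best defence has four parts.

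- **The code is only an example, and the default method is software behaviour that the SAP does not state.** True. But the text names no method either, so the example is the only specification there is.
- **The interval does widen.** A reader might infer from the low variance recovery that the model ignores within-subject dependence. The numbers do not support that: the default standard error is close to the subject-robust one, and two-sided coverage of the tested p at the null rate is about 0.92 to 0.96.
- **The estimation method is not the main cause of excess error.** A reader might treat it as a defect independent of the ILINK target. It is not. With ILINK unchanged, moving to quadrature raises the false-pass rate, so the default's shrinkage partly masks the target problem. Likewise, poor coverage of the rate at random effect zero would not show harm, because SAP 8.4.1 does not test that rate.
- **At low correlation little is lost.** This stands. At an ICC of about 0.1 or below, the error is within about a point of nominal and matches the exact test.

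What survives is narrower. The deciding analysis adds almost nothing to the test it is meant to check and, at higher correlation, errs on the side of passing.

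**Conclusion.** The point holds at moderate severity. As coded, the SAP 8.8 model combines a default fit that recovers roughly 0.3 to 0.65 of the between-subject variance with an interval centred above p. The result is almost no protection beyond the exact test: one-sided error of about 2–3% at an assumed ICC of 0.1 or below, and about 3.5–6% at 0.2–0.3, at or above the exact test. A subject-clustered robust interval stays at about 2–3%.

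The size rests on an ICC that the documents do not give, on assumed cluster-size patterns, and on a recoded algorithm. If vessels within a subject are nearly independent, the practical effect is negligible. The plan's intent, to let a dependence-aware analysis govern, is sound; the chosen implementation does not deliver it.

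**What to change.** In SAP 8.8, replace the deciding model with an intercept-only population-averaged logit GEE clustered on subject (PROC GENMOD or PROC GEE, REPEATED SUBJECT=id), using empirical standard errors with a named small-sample correction. Compare its lower 95% limit with 87.5%. This targets p as SAP 8.4.1 defines it. The correction matters because failures are few: about 252.7 × 0.06 = 15 expected at a 94% rate.

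If the mixed model is kept, specify METHOD=QUAD together with a success rate averaged over the estimated random-intercept distribution. Neither change should be made alone (Step 7).

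The cost is a few lines of SAP text and code, made before database lock. The real price is candour about power. If vessels are correlated, the deciding analysis has less than the stated 90%: about 0.82–0.88 at a 94% rate for ICC 0.1–0.3 with 133 subjects. Individual runs extend from 0.79 to 0.90, and the lowest value with 122 subjects is 0.73. SAP 7 should say so.

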5.4 PRIMARY AND SECONDARY ENDPOINTS AND ASSOCIATED HYPOTHESES

All study endpoints are described in Section 2.1 through Section 2.4. The following hypothesis will be evaluated for the primary endpoint:

H₀: $p \le 87.5\%$

 H_1 : p > 87.5%

Where *p* is the percentage of transections achieving a Grade 3 or lower hemostasis rating and 87.5% is set as a performance goal for the lower bound of acceptable hemostasis. A 95% confidence interval will be calculated for *p* based on the sample proportion of transections where Grade 3 or lower hemostasis was achieved using Clopper-Pearson's method and the lower limit of this confidence interval will be compared to 87.5% to evaluate the above hypotheses. A p-value will be determined based on exact binomial test.

Given that multiple transections per subject may occur, a sensitivity analysis will be performed using appropriate methods to account for the potential correlation among the outcomes of multiple transections within the same subject and procedure. Further details of this approach will be provided in the SAP.

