5.9.4 Primary and Secondary Endpoint Analyses

The number and percentage of vessels where hemostasis is achieved (≤ Grade 3) will be summarized and an exact 95% confidence interval will be estimated for each procedure group, procedure subgroup, and in total based on Clopper-Pearson's method. The performance goal hypothesis will be tested as described in Section 5.4.

The analysis of primary endpoint is based on the assumption of independence of hemostatic grades within subject and procedure. This assumption of independence and its impact on the overall study conclusion will be evaluated through sensitivity analyses and will be described in SAP.

Counts and percentages will be provided for type, size, and number of vessels transected, as well as for the grading scale distribution for all vessels transected, number of times ENSEAL X1 touch-ups were required, incidence of requirement for additional measures to obtain hemostasis on vessels (other advanced energy devices or hemostatic measures), and 5-point scale scores for various tasks completed by the ENSEAL X1 device (adhesiolysis, lymphatics or tissue bundles divided, tissue grasping, tissue cutting, or tissue dissection).

All device-related and procedure-related AEs reported during the study will be coded to MedDRA. All AEs will be summarized by MedDRA system organ class and preferred term by procedure group, procedure subgroup, and in total. Separate summaries will be provided for device-related and procedure-related AEs. Serious AEs will be summarized in a similar manner.

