1.2 Study Design

This prospective, single-arm, multi-center study will collect clinical data in a post-market setting by procedure group (upper gastrointestinal (GI), lower GI, and gynecological). Investigators will perform each procedure using the device in compliance with their standard surgical approach and the ENSEAL X1 and GEN11 IFUs.

Subjects will be consented and screened anytime during a period of 8 weeks prior to the date of surgery. Subjects will be considered enrolled when the ENSEAL X1 device has been attempted to be used for a vessel transection during upper GI, lower GI, or gynecological procedures. All enrolled subjects will be followed post-operatively through discharge and again at 28 days (\pm 14 days) post-surgery; therefore, from the surgery date to study exit, the duration will be approximately 6 weeks.

A minimum of 133 subjects (maximum of 149 subjects) will be included in the study from up to 16 surgery centers in the United States and/or European Union and/or United Kingdom. The enrollment is planned with the following procedure targets:

- A minimum of 77 subjects enrolled to a maximum of 89 subjects enrolled for upper GI procedures to achieve 27 vessel transections in each of the four procedure subgroups.
 Subjects will be enrolled to the following procedure subgroups with corresponding enrollment restrictions:
 - A minimum of 14 subjects enrolled to a maximum of 17 subjects enrolled for fundoplication (Nissen, anterior or posterior [Toupet]) or hiatal hernia procedures);
 - A minimum of 27 subjects enrolled to a maximum of 30 subjects enrolled for gall bladder procedures;
 - A minimum of 10 subjects enrolled to a maximum of 13 subjects enrolled for sleeve gastrectomy procedures;
 - A minimum of 26 subjects enrolled to a maximum of 29 subjects enrolled for small intestine resection procedures (also includes Roux-en-Y gastric bypass [RYGB] and biliopancreatic diversion with duodenal switch [BPD/DS]);
- A minimum of 28 subjects enrolled to a maximum of 30 subjects enrolled for lower GI procedures (e.g., large intestine resections); and
- A minimum of 28 subjects enrolled to a maximum of 30 subjects enrolled for gynecological procedures (hysterectomies associated with oophorectomies).

2 Treatment Assignment

This is a single-arm study where all enrolled subjects will have the ENSEAL X1 device utilized for transection of at least one vessel.

3 Randomization and Blinding Procedures

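### SAP 8.8 lets a random-intercept logit model decide success, but its reported rate is not the percentage of transections in H0, and clustered failures can turn a failed exact test into a pass

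*SAP*

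**What the plan says.** SAP 8.4.1 defines the tested quantity: p "is the percentage of transections achieving a Grade 3 or lower hemostasis rating and 87.5% is set as a performance goal". The denominator is all transections. Success requires the Clopper-Pearson 95% lower limit to exceed 87.5%, at one-sided level 0.025.

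Protocol 5.4 promises a sensitivity analysis "to account for the potential correlation among the outcomes of multiple transections within the same subject and procedure" and leaves the details to the SAP. Protocol 5.9.4 adds: "This assumption of independence and its impact on the overall study conclusion will be evaluated through sensitivity analyses".

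SAP 8.8 supplies the method: "A random intercept term at subject-level will be used in the generalized linear mixed model to account for the within subject correlation". The example code gives no estimation method and identifies the output to read: "LSMEANS group / CL ILINK; *The results of interest (95% CI of rate of hemostasis) are presented on the last two columns". If this result is not consistent with the exact test, "then the inference from the mixed model will be used to evaluate success".

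**The concern.** There are two problems, and they compound.

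**The target.** In a random-intercept logit model, LSMEANS with ILINK returns the inverse logit of the fixed intercept. That is the rate for a subject with random effect zero. When p is above 50% and there is any between-subject variance, this rate is higher than the percentage of transections. SAP 8.8 has no step that averages over the random effect.

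**The decision rule.** When the two analyses agree, the model's verdict is the verdict. When they disagree, the model wins. It is called a sensitivity analysis, but it decides every outcome of the study's only formal hypothesis.

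Clustering means less information, so a valid adjustment should lower the limit for p. This one can raise it, and a device that failed the exact test could then be declared to meet the performance goal.

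**Working it through.** **1. The plan's own figure.** SAP 7 states: "A sample size of at least 230 vessel transections is required to have a minimum of 90% power". With n = 230, H0 87.5% and an expected rate of 94.0%, the exact test needs at least 212 successes. P(X ≥ 212 | 0.875) = 1.61% and P(X ≥ 212 | 0.94) = 90.02%. The figure reproduces, under independence.

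**2. The theoretical gap.** Solve E[expit(b + σZ)] = 0.875 for b, with Z standard normal, and report expit(b). Here σ is the random-intercept SD.

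| σ | 0 | 0.5 | 1 | 1.5 | 2 | 3 |
|---|---|---|---|---|---|---|
| Correlation of outcomes within subject | 0 | 0.03 | 0.10 | 0.21 | 0.31 | 0.46 |
| Rate at random effect zero (%) | 87.5 | 88.5 | 90.8 | 93.3 | 95.5 | 98.2 |

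The code names no method, so the default residual pseudo-likelihood applies. It shrinks the variance, and the fitted shift is much smaller than this (step 4).

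**3. Worked example.** SAP 1.2 plans a minimum of 133 subjects. Assumed layout: 62, 45 and 26 subjects with 1, 2 and 3 vessels (62 + 90 + 78 = 230). Assumed result: 211 successes (91.7%), 19 failures.

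- Exact test: lower limit 87.40%, fail.
- All 19 failures in different subjects: fitted variance 0, model lower limit 87.35%, fail.
- Clustered failures: five subjects fail 1 of 1, four fail 1 of 2, two fail 2 of 2, three fail 1 of 3, one fails 3 of 3 (5 + 4 + 4 + 3 + 3 = 19). The pseudo-likelihood fit, with t on 230 − 133 = 97 df, gives variance 1.58, rate 92.7% and lower limit **88.02%, pass**.

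Cluster-adjusted limit for p on the same clustered data:

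- The sum over subjects of (successes − vessels × 0.9174)² is 25.80.
- Clustered variance = (133/132) × 25.80 / 230² = 0.000491.
- Binomial variance = 0.9174 × 0.0826 / 230 = 0.000329.
- Design effect = 1.49, so effective n = 230 / 1.49 ≈ 154.
- Clopper-Pearson at 91.7% with n = 154: lower limit **86.2%, fail**. A cluster-robust logit interval also gives 86.2%.

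**4. Simulation at true p = 87.5%.** Layout: 133 subjects with one vessel each, plus 97 more vessels placed at random. There were 20,000 replicates per σ (6,000 at σ = 3), and the Monte Carlo SE is at most 0.14 points (0.31 at σ = 3).

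| σ | 0 | 0.5 | 1 | 1.5 | 2 | 3 |
|---|---|---|---|---|---|---|
| Mean fitted ILINK rate (%) | 87.6 | 87.6 | 87.7 | 88.0 | 88.3 | 88.8 |
| False success, exact test (%) | 1.5 | 1.6 | 2.3 | 2.6 | 3.3 | 3.9 |
| False success, SAP model (%) | 1.6 | 1.7 | 2.6 | 3.1 | 4.4 | 6.3 |
| Model minus exact (points) | 0.1 | 0.1 | 0.3 | 0.5 | 1.1 | 2.4 |
| False success, effective-n Clopper-Pearson (%) | 1.5 | 1.5 | 2.1 | 2.0 | 2.5 | 2.3 |
| Overrides fail to pass (% of trials) | 0.04 | 0.08 | 0.27 | 0.57 | 1.12 | 2.38 |

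Overrides from pass to fail were at most 0.01% of trials.

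**5. Other assumptions.** A second layout was built from the protocol's enrollment minimums, with 6,000 replicates. At σ 0 / 1 / 2 it gives 1.6 / 2.1 / 3.8% for the exact test and 1.7 / 2.3 / 4.8% for the SAP model. With 121 subjects (about 1.9 transections each, as in SAP 7), beta-binomial clustering and 1,000 replicates, correlations of 0.1, 0.3 and 0.5 give 2.3, 3.6 and 5.3% for the exact test and 2.6, 5.0 and 8.8% for the SAP model.

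**The case against.** The core is hard to dispute, but several objections bear on its size.

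- **The increment is modest.** The exact test itself exceeds 2.5% under strong correlation. The model adds 0.3 points or less up to σ = 1 and about 1 point at σ = 2. The documents give no correlation and nothing shows that a high value is likely. This stands, and is why the result is given as a range.
- **The example is borderline.** It is one success short of the 212 needed. With the same 19 failures, milder clustering does not reverse the verdict: one subject failing 2 of 2 gives a lower limit of 87.25%, two such subjects 87.32%, and one failing 3 of 3 87.48%. This also stands. The example shows that a reversal can occur, and the simulation shows how often.
- **The code is only an example, and the text fixes no estimation method.** Full maximum likelihood by quadrature on the same data gives a rate of 99.2% with lower limit 87.54%, a bare pass. A different data set (121 subjects, 210 of 230) passes under pseudo-likelihood at 88.2% and fails under maximum likelihood at 80.7%, with a fitted rate of 99.8%. The direction of the decision error is therefore shown only for the default method. The wrong target is common to both, and a verdict that depends on an unstated option is itself a weakness.
- **The protocol does not forbid a mixed model.** True. The fault lies in the quantity read from it and in the override.

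**Conclusion.** The concern holds. The deciding analysis does not test the SAP 8.4.1 hypothesis, and under the default fit its overrides run almost entirely from fail to pass. False success stays near the nominal 2.5% up to σ of about 1 (correlation about 0.10). In the main layout it rises to 4.4% at σ = 2 and 6.3% at σ = 3. With no between-subject variance the effect is essentially nil.

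These sizes rest on assumed vessel counts per subject, an assumed range of correlation, default pseudo-likelihood and a Python implementation rather than SAS. The mismatch of target and the decision rule do not depend on those assumptions. The point should be fixed before the analysis is run.

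**What to change.** Make the deciding cluster-adjusted analysis a population-averaged interval for the proportion of transections, and compare its lower limit with 87.5%.

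- **Preferred:** Clopper-Pearson with effective n = 230 / design effect (using the actual number of transections), where the design effect is the subject-clustered variance over the binomial variance. Cap effective n at the actual count, so that the result is never more liberal than the exact test.
- **Alternative:** an intercept-only logit GEE with subject as cluster, working independence and robust standard errors. Simulated false success is 1.9 to 2.5% for σ 0 to 3 in the main layout.

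In the second layout both options reach 2.7% at σ = 2, within Monte Carlo error of 2.5%.

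The mixed model can stay as a supportive display. For clarity, the SAP should also state that the modelled event is hemostasis achieved, because the coding of OUTCOME is not given.

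Two smaller changes do less. Dropping the override stops the reversals but leaves the exact test at 3.3% and 3.9% for σ 2 and 3. Averaging the fitted rate over the random intercept gave 87.7% in the 121-subject example, where 91.3% was observed, so it does not recover p under the default fit.

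The cost is SAP wording and a few lines of code, plus power if correlation is strong. With the preferred interval, the simulated chance of success at a true 94% is about 90% at σ = 0, 87 to 88% at σ = 1 and 78 to 81% at σ = 2. The SAP model gives 90 to 91%, partly through its upward shift; at σ = 2, 5 to 6% of its fits did not converge. SAP 7 should say that its 90% power holds only under independence, or the sponsor should revisit the number of transections.
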